Appendix 7 – Further details on social research instruments

7.1. User research

The aim of this research activity is to understand the user journey for Daily Contact Testing within intervention arm participants. We need to identify any residual risks to effective delivery and mitigate these before rolling out the trial. We also need to understand how the DFE can communicate effectively to ensure take-up for DCT in these settings is high.

Main objectives as follows:

- 1. Understand the user journey of DCT within secondary school and college settings, including how this varies in different institutions
- 2. Identify any risks or blockers that will stop DCT being implemented.
- Inform learning from Phase 1 of the trial to improve the implementation of Phase 2. In phase 2, to inform policy recommendations about the use of DCT in secondary schools and colleges.
- 4. Ensure policy relating to testing in special schools reflects the needs, experiences and challenges of special schools

Participants

Staff (teaching and non-teaching) at participating intervention arm institutions involved in management / implementation of Daily Contact Testing.

Two waves of user research interviews will be delivered in phase 1 and a further two waves in phase 2. Interviews will be conducted at the start of the trial and near to the end of the trial.

In Phase 1 we expect to conduct a user research interview in all consenting schools (c. 5 initial and 5 follow up interviews). In phase 2 we will conduct ten initial interviews and follow up interviews. No more than one research interview will be conducted per school, to minimise research burden.

Targeting

Schools will be selected based on the available pool of volunteers to maximise potential insight. For phase 1 we expect this to be all consenting schools. For phase two we will select schools to approach for user research interviews where there is most scope for differing experiences that we can learn from: e.g. different school types; different levels of disadvantage; etc.

Delivery mechanism

Online or telephone interviews, no longer than 20-30 minutes.

Staff participants will be recruited through consenting schools, via the lead contact between the school and the trial administrators. We expect that consenting schools will confirm an appropriate person to be interviewed and contact details for that person will be shared with the research team.

User research topics

Decision making and participation

- Initial reaction to the trial invitation
- Reasons for joining the trial and decision-making process
- Understanding of DCT (what is it?; why is it being trialled? etc)

DCT delivery (planned / enacted)

- Logistics of delivery in the school (e.g. all activities undertaken in-house, sub-contracted out, or mixture; number of testing centres; location of testing)
- Process of delivering testing in the school
- Process of what happens when there is a positive DCT result
- Experiences of reporting testing data results

DCT engagement

- Communication about DCT with pupils, parents, and staff including how consent is being managed, any post-result conversations / discussions with pupils
- Any challenges helping pupils through testing
- Experiences with self-isolating vs DCT participating pupils (e.g. any insight into reasons for preferring self-isolation; school's preference; etc.)

Anticipation / reflections

- Anything expected to work well / that worked more smoothly than anticipated
- Any expected / experienced key pain points
- Views on what could be changed to work effectively
- Expected obstacles, if any, to scaling DCT: for schools, for pupils

7.2. In-depth qualitative interviews

The aim of this research activity interviews is to generate rich detail on the experience of testing, perspective / attitudes towards the testing (and DCT in particular), and behavioural responses to test results. In-depth interviews are designed to explore *why* participants hold particular perspectives or act in particular ways. They are not designed to be generalisable, but instead create a more holistic understanding of participants' experiences in the intervention or control schools.

Participants

The following sub-groups will be recruited as interviewees:

- Close contacts, intervention DCT
- Close contacts, intervention self-isolation
- Close contacts, control
- Parents, intervention DCT
- Parents, intervention self-isolation
- Parents, control
- Staff, intervention

Note that close contacts could be staff members, not just pupils, depending on positive cases.

Final total of interviews conducted will be dependent on number of cases found and number of consenting participants, but are aimed to be as follows:

- 12-15 each Close contacts, DCT; Parents, DCT
- 8-12 each Close contacts, intervention self-isolation
- 8-12 each Close contacts, control; Parents (intervention self-isolation & control); Staff, intervention

Targeting

Our selection of interviewees will be limited by where positive COVID cases arise (and thus who are close contacts), but in principle we will recruit interviewees to get a mix of gender, ethnicity and education setting types (ensuring representation of schools serving minority ethnic and low income communities) to better understand any idiosyncratic issues for different sub-populations.

Delivery mechanism / recruitment

For close contacts and parents, recruitment will be brokered a letter home to parents asking for consent to participate. The same letter will be used for the DCT 7 day survey and in-depth interviews, to minimise burden. Staff will be recruited via a request through their schools.

Participants will be invited to take part in recorded online or telephone interviews (20 to 30 minutes) outside of school opening hours and will receive an online voucher as reimbursement for their time.

Main interview topics

For all close contacts:

- Information and advice received
- Support received
- Willingness to share close contact details
- Preference for daily testing vs self-isolation
- Experiences of DCT / self-isolation
- Behaviour during DCT / self-isolation
- [Intervention only] Reasons for opting for DCT or self-isolation

For parents (in addition to relevant elements of above):

- Willingness to consent to testing
- Perspectives on safety of testing

For staff (in addition to relevant elements of above):

• Classroom impact of testing - DCT participants attending vs isolating; potential workforce burden impacts on wider school activity

Interview schedules

All interviews will be preceded by a standard introduction the research, explanation of the process and participants' rights.

Close contacts, Intervention Daily Contact Testing sample

I would like to start by asking you about your experiences of daily testing for COVID-19.

- What made you agree to carry daily testing instead of self-isolating?
- What is good about self-isolation? What is not so good about self-isolating?
- What is good about daily testing? What is not so good about daily testing?
- What happened on the day you were told you had been in contact with someone with the virus?

Experiences of testing

- What happened on the first day that you took a test? Can you tell me about anything that changed?
- Were there any times that you didn't get tested?
- What happened on those days?
- What was the most difficult part of having to be tested daily?
- What did you do to help you overcome any problems?

Behaviour during testing

- How did you feel when you received a negative test result? How did it affect your life?
- What, if anything, did you do differently at school on the days you got a negative test?
- Can you tell me about anything you do differently outside school on the days you got a negative test?
- Can you tell me about anything you do differently at home on the days you got a negative test?
- Did you take more or less precautions to reduce infection on the days you got a negative test?
- Why / why not?

[This section only for DCT participants required to self-isolated because of a positive test] How did you feel when you received a positive test result? How did it affect your life? There's loads of guidance to do with self-isolation, and we know people can find some of it tricky.

- What does the term self-isolation mean to you?
- What steps did you take?
- Can you tell me about any times when you had to leave the house?
- Can you tell me about any times when you had visitors?
- Can you tell me about any times it was hard to stick to the guidance?
- What was the most difficult part of having to self-isolate?
- What did you do to help you overcome any problems?
- What would have helped you to be able to follow the advice around selfisolating?
- Do you think having to self-isolate had any impact on your health, wellbeing or education in anyway?

What, if anything, did you do differently in the home while you were self-isolating?

- Did you take any extra precautions to reduce infection in the home?
- Why/why not?

What support did you have to help you with daily testing and self-isolation?

- What did you think of the support?
- What support did you need? / what was missing?

What information or advice did you and your family have about daily testing and self-isolation?

- Where did you look for information or advice?
- What information did you find most reliable?
- What did you think about the information you found?
- Was anything unclear or confusing?
- Was anything missing?

Have you had to take a test or self-isolate before?

[IF YES]

- How did your experiences of daily testing and self-isolation compare with any other times you have been in contact with a positive case?
- What was different?
- What was better/worse?

If you were told that you had been in contact with a positive case in the future, would you choose to do daily testing again or to self-isolate instead?

• What might influence this decision? What could be done to make it better / easier for people to test/isolate?

If you had a positive test in the future and you knew that your contacts would be able to have daily testing (instead of self-isolating), would this affect how willing you are to share their contact details?

Is there anything else you would like to say?

Close contacts, Intervention self-isolating sample

Can you start off by telling me about your experiences of having to self-isolate for 10 days?

- What made you decide to carry out self-isolation instead of 7 days daily testing?
- Did you have any concerns about daily testing that made you choose self-isolation?
- Did you have any concerns about self-isolating?
- What happened on the day you were told you had been in contact with someone with the virus?

There's loads of guidance to do with self-isolation, and we know people can find some of it tricky.

- What does the term self-isolation mean to you?
- What steps did you take?
- Can you tell me about any times when you had to leave the house?
- Can you tell me about any times when you had visitors?
- Can you tell me about any times it was hard to stick to the guidance?
- What was the most difficult part of having to self-isolate?
- What did you do to help you overcome any problems?
- What would have helped you to be able to follow the advice around self-isolating?
- Do you think having to self-isolate had any impact on your health, wellbeing or education in anyway?

Can you tell me anything you did differently in the home during the 10/14 days that you were in self-isolation?

- Did your family take any extra precautions to reduce infection in the home?
- Why/why not?

What information or advice did you and your family have about self-isolating?

- Where did you look for information or advice?
- What information did you find most reliable?
- What did you think about the information you found?
- Was anything unclear or confusing?
- Was anything missing?

What support did you have to help you to self-isolate?

- What did you think of the support?
- What support did you need? / what was missing?

If you were informed that you had been in contact with a positive case again, would you be willing to complete seven days testing / isolating instead of self-isolation for 10/14 days?

- Why?
- What might influence this decision?
- What could be done to make it better / easier for people to test/isolate?

Is there anything else you would like to say?

Close contacts, control sample

Can you start off by telling me about your experiences of having to self-isolate for 10 days?

- Did you have any concerns about self-isolating?
- What happened on the day you were told you had been in contact with someone with the virus?

There's loads of guidance to do with self-isolation, and we know people can find some of it tricky.

- What does the term self-isolation mean to you?
- What steps did you take?
- Can you tell me about any times when you had to leave the house?
- Can you tell me about any times when you had visitors?
- Can you tell me about any times it was hard to stick to the guidance?
- What was the most difficult part of having to self-isolate?
- What did you do to help you overcome any problems?
- What would have helped you to be able to follow the advice around self-isolating?
- Do you think having to self-isolate had any impact on your health, wellbeing or education in anyway?

Can you tell me anything you did differently in the home during the 10/14 days that you were in self-isolation?

• Did your family take any extra precautions to reduce infection in the home?

• Why/why not?

What information or advice did you and your family have about self-isolating?

- Where did you look for information or advice?
- What information did you find most reliable?
- What did you think about the information you found?
- Was anything unclear or confusing?
- Was anything missing?

What support did you have to help you to self-isolate?

- What did you think of the support?
- What support did you need? / what was missing?

If you were informed that you had been in contact with a positive case again, would you be willing to complete seven days testing / isolating instead of self-isolating for 10/14 days?

- Why?
- What might influence this decision?
- What could be done to make it better / easier for people to test/isolate?

Is there anything else you would like to say?

Parents, intervention Daily Contact Testing sample

I would like to start by asking you about your experiences of [PUPILNAME] doing daily testing for COVID-19.

- What made you agree for [PUPILNAME] to carry daily testing instead of self-isolating? What were some of the factors that influenced your decision?
- What are your feelings about self-isolation?
- What are your feelings about daily testing?

Experiences of testing

- What happened on the day you were told [PUPILNAME] had been in contact with someone with the virus?
- What happened on the first day that they took a test? Can you tell me about anything that changed?
- Were there any times that [PUPILNAME] didn't get tested? What happened on those days?
- What was the most difficult part of [PUPILNAME] having to be tested daily?
- What did you do to help you overcome any problems?

Behaviour during testing

- Did you and [PUPILNAME] discuss the test process and their test results much? What did you talk about?
- How did you feel when [PUPILNAME] received a negative test result?
- Do you notice [PUPILNAME] do anything differently at school, outside school, or at home on the days they got a negative test?
- Did you do anything differently on the days [PUPILNAME] got a negative test result?

[This section only for parents of DCT participants required to self-isolated because of a positive test]

How did you feel when [PUPILNAME] received a positive test result? How did it affect your life?

What does the term self-isolation mean to you?

Can you tell me about your experiences of [PUPILNAME] having to self-isolate?

- What steps did you take?
- What was the most difficult part of having to self-isolate?
- What did you do to overcome any problems you had?
- What would have helped you overcome any problems that you had?
- Do you think having to self-isolate had any impact on [PUPILNAME]'S health, wellbeing or education in anyway?

There's loads of guidance to do with self-isolation, and we know people can find some of it tricky.

- Can you tell us about any times that you [PUPILNAME] had to leave the house?
- Can you tell us about having visitors?

What, if anything, did you do differently in the home while [PUPILNAME]'s were self-isolating?

- Did you take any extra precautions to reduce infection in the home?
- Why/why not?

What information or advice did your family have about daily testing and self-isolation?

- Where did you look for information or advice?
- What information did you find most reliable?
- What did you think about the information you found?
- Was anything unclear or confusing?
- Was anything missing?

Have you had to take a test or do self-isolation before?

[IF YES]

- How did your experiences of daily testing and self-isolation compare with any other times you have been in contact with a positive case?
- What was different?
- What was better/worse?

If you were told that [PUPILNAME] had been in contact with a positive case in the future, would you choose to do daily testing again or to self-isolate instead?

• What might influence this decision? What could be done to make it better / easier for people to test/isolate?

If you had a positive test in the future and you knew that your contacts would be able to have daily testing (instead of self-isolating), would this affect how willing you are to share their contact details?

Is there anything else you would like to say?

Parents, intervention self-isolation sample

I would like to start by asking you about your experiences of [PUPILNAME] having to self-isolate for 10 days.

- What made you decide to carry out self-isolating instead of 7 days daily testing?
- What are your feelings about self-isolating?
- What are your feelings about daily testing?
- What happened on the day you were told [PUPILNAME] had been in contact with someone with the virus?

There's loads of guidance to do with self-isolation, and we know people can find some of it tricky.

- What does the term self-isolation mean to you?
- What steps did you and [PUPILNAME] take?
- Can you tell me about any times when [PUPILNAME] had to leave the house?
- Can you tell me about any times when you had visitors?
- Can you tell me about any times it was hard to stick to the guidance?
- What did you do to help you overcome any problems?
- What would have helped you to be able to follow the advice around self-isolating?
- Do you think having to self-isolate had any impact on [PUPILNAME]'S health/wellbeing/education in anyway?

What information or advice did your family have about daily testing and self-isolation?

- Where did you look for information or advice?
- What information did you find most reliable?
- What did you think about the information you found?
- Was anything unclear or confusing?
- Was anything missing?

If you were told that [PUPILNAME] had been in contact with a positive case in the future, would you choose to do daily testing again or to self-isolate instead?

• What might influence this decision? What could be done to make it better / easier for people to test/isolate?

Is there anything else you would like to say?

Parents, control sample

I would like to start by asking you about your experiences of [PUPILNAME] having to self-isolate for 10 days.

- What are your feelings about self-isolating?
- What happened on the day you were told [PUPILNAME] had been in contact with someone with the virus?

There's loads of guidance to do with self-isolation, and we know people can find some of it tricky.

- What does the term self-isolation mean to you?
- What steps did you and [PUPILNAME] take?
- Can you tell me about any times when [PUPILNAME] had to leave the house?
- Can you tell me about any times when you had visitors?

- Can you tell me about any times it was hard to stick to the guidance?
- What did you do to help you overcome any problems?
- What would have helped you to be able to follow the advice around self-isolating?
- Do you think having to self-isolate had any impact on [PUPILNAME]'S health/wellbeing/education in anyway?

What information or advice did your family have about daily testing and self-isolation?

- Where did you look for information or advice?
- What information did you find most reliable?
- What did you think about the information you found?
- Was anything unclear or confusing?
- Was anything missing?

If you were told that [PUPILNAME] had been in contact with a positive case in the future, would you choose to do daily testing again or to self-isolate instead?

• What might influence this decision? What could be done to make it better / easier for people to test/isolate?

Is there anything else you would like to say?

Staff, intervention arm schools

Have you been involved in delivering testing at the school?

[IF YES]

- Can you tell me about you experiences?
- To what extent has being involved in testing impacted on your other duties?

What information or advice did you receive about daily testing?

- What information and guidance did you receive from the school about daily testing?
- Did you look for additional information or advice? What information did you find most reliable?
- To what extent was it clear why daily testing was being undertaken?

How would you describe the impact of testing at your school?

- Did anything unexpected happen?
- Is there anything you think has gone particularly well?
- Is there anything you think has gone badly, or that you would do differently?
- What was your reaction when you heard about daily testing being implemented at the school?
- To what extent has your view changed?

Impacts of testing on behaviour

- Do you know anyone in the school who was taking daily tests?
- How do you feel about having pupils in school who had been identified as a contact of a positive case, but tested negative themselves? Why?
- Did you do anything differently at school while the daily testing has been going on?

Overall, to what extent do you think daily testing is suitable for your schools?

- Are there any clear benefits you think are important?
- Are there any clear drawbacks you think are important?
- Is there anything you think is specific to your school, or your type of school, that makes daily testing more or less effective?

Is there anything else you would like to say?

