Primary Attack Rate	The proportion of first-order contacts of the index case who themselves go on to be diagnosed with COVID-19
Secondary Attack Rate	The proportion of second-order contacts of the index case who themselves go on to be diagnosed with COVID-19

Figure 1: Definitions used for the chain of transmission

1. Rationale

When a person in a school / FE college¹ is diagnosed with COVID-19, first-order close contacts are required to self-isolate for 10 days. In schools, some groups of these close contacts (often managed as 'bubbles') may be quite large (e.g. a whole year group of over 250 pupils) and self-isolation has negative impacts on the education, psychological health and wellbeing of those affected². There is some evidence that suggests that compliance with self-isolation outside the school setting may be as low as 11% in asymptomatic contacts³ (although this may have improved since self-isolation has become a legal requirement). Modelling data shows daily testing of first-order contacts, using rapid lateral flow tests, could avert a similar level of onward virus transmission as self-isolation. In addition, recent work, has found that contacts identified by Test and Trace in the same household are more likely to become infected than first-order contacts at work, school or elsewhere. Primary age children are less likely to infect someone else and contact in schools with an infected child and are at a lower risk of transmission⁴.

It is proposed that when a positive case is detected, first-order close contacts will be offered the choice of being tested daily using rapid Lateral Flow Device antigen testing as an alternative to the requirement to self-isolate. A first-order contact with a negative test at the start of the school day can remain in school. However, they will be advised to self-isolate outside school. A person who tests positive with LFD will follow national protocols and self-isolate for ten days. This process is referred to here as Daily Contact Testing (DCT). DCT will enable the pupil's education to continue and reduced the health and wellbeing impacts of self-isolation.

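### The interview prompt naming health, wellbeing and education is not asked in parallel: no test-negative daily-testing contact or parent receives it

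*Protocol*

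**What the plan says.** The Rationale (Protocol, Section 1) makes a comparative claim: "DCT will enable the pupil's education to continue and reduced the health and wellbeing impacts of self-isolation".

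Section 7.2 of Appendix 7 sets out six interview schedules for close contacts and parents, and one for staff. Contacts who isolate, whether in the intervention arm or in the control arm, are all asked "Do you think having to self-isolate had any impact on your health, wellbeing or education in anyway". Parents of both groups are all asked "Do you think having to self-isolate had any impact on [PUPILNAME]'S health/wellbeing/education in anyway".

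The schedule for contacts on daily contact testing (DCT) contains the same question, but below the instruction "This section only for DCT participants required to self-isolated because of a positive test". The schedule for parents of DCT pupils has the parent version, "Do you think having to self-isolate had any impact on [PUPILNAME]'S health, wellbeing or education in anyway", below an equivalent restriction.

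Outside the restricted part, every DCT contact is asked, among other things, "What is good about daily testing? What is not so good about daily testing", "What was the most difficult part of having to be tested daily" and "How did you feel when you received a negative test result? How did it affect your life".

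**The concern.** The claimed benefit compares two policies, but the only prompt that names the claimed domains is worded about one of them. DCT is not free of restrictions that could affect wellbeing. Sections 3.1 and 4.2.1 require test-negative participants to isolate outside school, and on days without a test, such as weekends. The question is therefore relevant to them too, yet it is put to them neither about testing nor about this partial isolation.

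A prompt that names specific domains can bring out remarks that a general one does not. If isolators talk about wellbeing or education and DCT participants do so less, the analyst cannot tell whether their experience differed or only the questions did. At stake is the readability of the qualitative evidence on one part of the case for DCT.

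**Working it through.** No formula applies. The check compares the six contact and parent schedules in Section 7.2 on the one item that names health, wellbeing or education.

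| Schedule | Who is asked the item | What it asks about |
|---|---|---|
| Contacts, intervention, self-isolating | everyone | isolation |
| Contacts, control | everyone | isolation |
| Parents, intervention, self-isolating | everyone | isolation |
| Parents, control | everyone | isolation |
| Contacts, DCT | only after a positive test | isolation |
| Parents, DCT | only after a positive test | isolation |

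Count: everyone in 4 of 6 schedules, positive-test cases only in 2 of 6, and test-negative DCT participants or their parents in 0 of 6. No schedule has a version about daily testing.

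The end of the restricted block is not marked in the DCT schedules. The item follows directly on other questions about having isolated, and comes before the schedule returns to general questions. Its wording also fits only someone who isolated. It is therefore read as inside the block.

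Next, does another instrument fill the gap? The survey in Appendix 2 covers activities, test results, confidence in the results, preference between the two options, and demographics. It has no health or wellbeing item. The user-research topics in Section 7.1 and the staff schedule do not name these domains as an effect on pupils. School days missed, a co-primary endpoint, bear on education but not on health or wellbeing.

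Last, what do test-negative DCT participants get instead? Contacts get the three questions quoted above, and are asked how they overcame problems, what happened on days without a test, and what support was missing. Those who had tested or isolated before are asked what was better or worse. DCT parents are asked their feelings about daily testing, what changed, what was most difficult, and the same comparison with earlier episodes. These items draw out burden and downsides. None names health, wellbeing or education.

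**The case against.** The strongest reply is that the interviews already look for the negatives of DCT. The open items listed above do so for contacts and parents. Intervention-arm isolators are asked about concerns with daily testing, and staff about its drawbacks. DCT contacts are also asked what is good about isolating. The health and wellbeing item asks about any impact, so it is neutral in direction and is not a harms prompt. Section 7.2 says the interviews are meant to explore reasons and experience and do not aim at generalisable findings. No planned analysis compares answers to this item between groups.

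Most of this stands, and it rules out a stronger reading. A reader might infer that there is no account of DCT to set against isolation, or that the interviews favour DCT by design. The schedules do not support either.

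A reader might also apply the 5% test positivity assumed in Section 3.9 to the planned DCT interviews (12 to 15 contacts and 12 to 15 parents) and conclude that nearly all would miss the item. That does not follow. Section 3.8 says the sample will include people with positive and with negative results, so a planning rate for all DCT contacts does not predict who is interviewed.

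The reply does not cover the named domains themselves. Section 7.2 seeks a rounded picture of experience in intervention and control schools, and on this topic that picture rests on a prompt that one group does not receive. That the findings need not generalise does not remove the difficulty of reading the accounts together.

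**Conclusion.** The point holds as a minor one. The prompt on health, wellbeing and education is not parallel across schedules: all self-isolating and control contacts and parents receive it, no test-negative DCT contact or parent does, and no version asks about daily testing. Accounts in these domains therefore cannot be set side by side, although the Rationale cites them as a benefit of DCT.

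The size is the schedule count of 4, 2 and 0 out of 6. The documents do not allow a count of interviews affected. The conclusion assumes that interviewers follow the schedules as written; an interviewer who probes freely would narrow the gap. No endpoint, sample size or between-arm test is affected.

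**What to change.** In the unfiltered part of both DCT schedules, add one neutral question, for example: *Do you think daily testing, including staying at home outside school, had any impact on your (or the pupil's) health, wellbeing or education?* Keep the existing isolation item for those who tested positive, so that they answer about both. Report the answers next to those of the isolating and control samples.

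The cost is one line in each of two schedules and about one extra minute per DCT interview. Randomisation, testing and endpoints stay as they are.
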